### **1.2 Secondary Objectives**

Determine if pioglitazone decreases serum thyroglobulin in patients with thyroid carcinomas that contain the PAX8-PPARgamma fusion gene.

Measure toxicities experienced by patients with PAX8-PPARgamma fusion gene-positive thyroid carcinomas treated with pioglitazone.

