## 9. STATISTICAL CONSIDERATIONS

### 9.1 Study Design

This is a phase II study with a primary endpoint of response (CR or PR per RECIST criteria) to pioglitazone therapy. Best response during the 24 weeks on Pioglitazone therapy will be assessed in thyroid cancer patients with metastatic disease who have CT evidence of disease progression in the prior 14 months. It is expected that without treatment there would be no improvement in the disease in these patients. This drug will be of interest to pursue alone or in combination with other therapies with a 40% best response rate. Accrual of 14 evaluable patients at a 95% two-sided significance level will provide 87% power to detect a 40% response rate compared to the expected 5% or less. A patient will be evaluable if they remain on treatment for 11 weeks or they are removed from study due to progression or toxicity.

Secondary endpoints include toxicity, serial measurements of serum thyroglobulin, lipid content of metastases determined by MRI, and radioiodine uptake. Since this drug is well known and used in humans we do not expect toxicity to be a problem. However, toxicity will be observed and reported throughout the trial as this is the first trial with Pioglitazone in this patient population.

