### 9.2 Analysis Plan

All CT and MRI scans will be reviewed centrally through the University of Michigan Department of Radiology. The primary endpoint analysis will report the best response percent and corresponding 95% binomial confidence interval. Only those patients who have measurable disease present at baseline (an eligibility criterion), have received at least 11 weeks of therapy and have had their disease re-evaluated; or who come off therapy due to progressive disease or unacceptable adverse events at any time, will be considered evaluable for response. Each evaluable patient will be assigned one of the following categories: 1) complete response, 2) partial response, 3) stable disease, 4) progressive disease, 5) early death from malignant disease, 6) early death from toxicity, 7) early death because of other cause, or 8) unknown (not assessable, insufficient data). All of the patients who met the evaluability criteria will be included in the analysis of the primary endpoint. Patients in response categories 1-2 while on treatment will be considered responders to treatment. Thus, an incorrect treatment schedule or drug administration does not result in exclusion from the analysis of the response rate.

All patients enrolled and who receive any drug will be assessable for toxicity from the time of their first treatment with study drug. Toxicity will be described by grade and type using frequencies and percentages.

Serum thyroglobulin will be reviewed for the 12 months prior to enrollment, and will be obtained at enrollment and at  $12\pm 1$  and  $24\pm 1$  weeks of therapy. The changes in thyroglobulin before pioglitazone treatment and after treatment will be summarized overall and by response. Patient profile plots will be created to descriptively show the serum thyroglobulin values over time. Means and standard deviations or medians and minimum and maximums will be used to summarize all patients at each time and changes from baseline at the later times. Similarly, statistical descriptions of the response group and the non-response groups will be reported.

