The changes in target lesion lipid content at  $24\pm 1$  weeks (or the end of treatment, whichever comes first), compared to pre-study, will be summarized overall and by response. Means and standard deviations or medians and minimum and maximums will be used to summarize the overall patient population at each time. Similarly, statistical descriptions of the response group and the non-response groups will be reported. A paired t-test (or paired Wilcoxon rank test if the data distribution requires it) will be used to compare the changes in target lesion lipid content after treatment to the baseline lipid content in the overall study population with both measurements. In an exploratory analysis, a logistic model will be used with the outcome being response and the independent predictor will be the lipid content change from baseline. The changes in target lesion radioiodine uptake will be summarized overall and by response in a follow-up protocol available to subjects completing this study.

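### Section 1.2 asks whether pioglitazone lowers serum thyroglobulin, but section 9.2 plans only descriptive summaries, with no interval, test, relative scale or rule for choosing mean or median.

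*Combined protocol and SAP*

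**What the plan says.** The objective in section 1.2 is worded as a question with a direction: "Determine if pioglitazone decreases serum thyroglobulin in patients with thyroid carcinomas that contain the PAX8-PPARgamma fusion gene". Section 9.1 gives the measure its standing: "Secondary endpoints include toxicity, serial measurements of serum thyroglobulin".

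Section 9.2 (and section 8.3 in near-identical terms) describes the data. "Serum thyroglobulin will be reviewed for the 12 months prior to enrollment, and will be obtained at enrollment and at" weeks 12 and 24 of therapy, each with a one-week window. The analysis then has three parts:

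- A summary of change: "The changes in thyroglobulin before pioglitazone treatment and after treatment will be summarized overall and by response".
- Plots: "Patient profile plots will be created to descriptively show the serum thyroglobulin values over time".
- Summary statistics: "Means and standard deviations or medians and minimum and maximums will be used to summarize all patients at each time". The same sentence goes on to cover changes from baseline at the later visits, so a within-patient change is planned. The statistics are also to be given for responders and non-responders.

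No interval, test, threshold, lead time point or measurement scale is named, and nothing says when means or medians will be used.

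For target lesion lipid content on the optional MRI, section 9.2 adds inference: "A paired t-test (or paired Wilcoxon rank test if the data distribution requires it) will be used". An exploratory logistic model of response on lipid change follows.

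**The concern.** The objective and the analysis do not match. A question about whether a marker falls calls for an estimate of the fall with a statement of its precision, and section 9.2 plans the first only loosely and the second not at all. Small numbers do not explain the gap. The plan is willing to test lipid content, which is optional, while thyroglobulin is drawn under the study calendar for everyone and section 2.3 describes it as an established marker.

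Two practical consequences follow. First, the open choice between mean and median can change the message. Tumour marker levels can differ greatly between patients, and a mean of absolute changes then mostly reflects the patients with the highest levels. Second, there is no control arm, and section 3.1.3 requires recent progression, so levels may be rising at entry. Change from baseline alone would mix that trend with any drug effect. The plan does collect the prior 12 months, but does not say how the earlier and later changes will be put on a comparable footing.

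**Working it through.** **The plan's own figure.** The only sizing figure is 87% power for response in section 9.1 (14 patients, 40% against 5%, two-sided 0.05). Exact binomial:
- P(X ≥ 3 | 14, 0.05) = 0.030, above 0.025, so the rule is at least 4 responders.
- P(X ≥ 4 | 14, 0.05) = 0.0042.
- P(X ≥ 4 | 14, 0.40) = 0.876.

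The figure reproduces, but it covers response only. Nothing is stated for thyroglobulin, so every variability figure below is an assumption.

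**Does mean or median matter?** Simulated trials assumed:
- n = 14 and lognormal levels;
- a true 40% fall in every patient;
- between-patient log SD of 1.0 to 2.0;
- per-measurement log SD of 0.3 to 0.5, so the log-change SD is √2 × 0.3 = 0.42 to √2 × 0.5 = 0.71.

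| Quantity | Between-patient log SD | Result |
|---|---|---|
| Mean change on the original scale has the wrong sign | 1.5-2.0 | about 1-10% of trials |
| Median change has the wrong sign | 1.0-2.0 | at most about 2% of trials |
| Highest patient's share of summed baseline level, typical | 1.0-2.0 | about 24-45% |
| Power, signed-rank test on original-scale change | 1.0-2.0 | about 55-95% |
| Power, paired t-test on log ratio | 1.0-2.0 | about 70-99% |

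A paired t-test on original-scale change would have about 11-47% power at log SD 1.5 to 2.0. The plan contains no such test, so that figure shows only what skew does to a mean.

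**What would a log-ratio analysis deliver?** For SD s of the log change and n patients, the 95% CI for the geometric mean ratio is the estimate times or divided by exp(t × s/√n). With n = 14, t = 2.160 and √n = 3.742:
- s = 0.5: exp(2.160 × 0.5/3.742) = exp(0.289) = 1.33
- s = 0.8: exp(0.462) = 1.59
- s = 1.0: exp(0.577) = 1.78

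A 40% fall is a log change of ln 0.6 = −0.511. The noncentrality is 0.511 × 3.742/s:
- s = 0.5: 3.82, power 94%
- s = 0.8: 2.39, power 60%
- s = 1.0: 1.91, power 42%

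If antibodies or missing values left 10 usable patients (also an assumption), t = 2.262 and √n = 3.162. The factor is 1.43 at s = 0.5 and 2.04 at s = 1.0, and power is 82% and 30%.

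**The case against.** The strongest reply is that descriptive analysis of a secondary marker in a single-arm trial of about 14 patients is a legitimate choice, and that what is planned already shows most of what matters. Individual profiles and summarised changes at weeks 12 and 24 will show whether levels fell. If mean and SD are reported, a reader can derive an interval as mean ± 2.16 × SD/√14. A p-value would not attribute a fall to the drug without a control arm. Sections 8.3 and 9.2 also summarise the change before treatment as well as after it. All of this stands.

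It therefore rules out three stronger readings that a reader might infer:

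- **That the objective cannot be answered, or that no within-patient estimate is planned.** Changes from baseline are explicitly included, and their direction will be visible.
- **That the plan commits to the original scale.** Section 9.2 names no scale, and the median option gives real protection against skew.
- **That the pre-treatment trend is ignored.** It is to be summarised. What is missing is a common scale for setting it beside the on-treatment change.

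The contrast with lipid should not be pressed too far either. Section 7.1 makes a directional prediction for lipid, which may explain the test, and section 9.1 lists lipid as a secondary endpoint too. Nor do the documents establish that fewer patients will have lipid data, since some thyroglobulin values will be lost to antibodies.

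What the reply does not remove is that no precision, scale or choice of summary is fixed in advance. If medians with minimum and maximum are reported, no interval can be recovered from them.

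**Conclusion.** The point holds as a gap in pre-specification. A directional secondary objective has an analysis plan with no interval, test or relative scale and an open choice of summary. The primary endpoint is unaffected.

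The size is modest. The risk of a misleading sign is about 1-10%, arises only if the original-scale mean is chosen, and depends on assumed strong skew. The permitted median cuts it to about 2% or less. The gain in power from the log scale over a signed-rank test is real but not large.

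The main benefit is a planned estimate with a stated precision. At n = 14 its interval is usefully narrow for a log-change SD of 0.5 to 1.0. Power over that range runs from good to poor, so a non-significant test would say little. The log-change SD, the between-patient SD, the 40% fall and the number of usable patients are all assumptions outside the documents.

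Severity: minor. Label: free improvement.

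**What to change.** Add to section 9.2, for patients with both values and no interfering antibodies:

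1. **Main estimate.** Analyse log(week 24 / baseline). Report the geometric mean ratio with its 95% CI as the lead result. Add a paired t-test, or a signed-rank test if the distribution requires it, as for lipid.
2. **Supportive estimates.** Repeat at week 12 and for the last on-treatment value. The last-value analysis matters because section 4.3 stops treatment at progression, so week 24 values may be missing for those who do worst. It mixes treatment durations and should stay supportive.
3. **Low values.** State the value assigned to results below the assay limit. Section 8.2.2 ties complete response to a level of 0.5 ng/mL or less, so very low results are foreseen, and a log ratio needs a rule for them.
4. **Pre-treatment trend.** Show each patient's change over the prior 12 months beside the on-treatment change, on the same log scale and with the time span given. Keep this descriptive: the number of historical values is not specified, and three planned values per patient cannot carry much slope modelling.
5. **Numbers.** Report how many patients are excluded for antibodies or missing values.

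Keep the profile plots, medians and ranges. The cost is a few lines of text and one extra analysis, with no new visits, assays or patients.

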### **2.3 Correlative Studies Background**

Serum thyroglobulin levels will be measured. Thyroglobulin is a well established tumor marker in thyroid cancer. Serial serum thyroglobulin measurements are part of the accepted standard of care for thyroid cancer management (5).

Optional for enrolled patients who consent: MRI will be used to assess fat content of the cancer metastases. MRI is an accepted non-invasive method to assess tissue fat content. Our mouse tumor model data indicate that pioglitazone causes a lipogenic response (i.e. the mouse tumors accumulate lipid droplets), which reflects the PPAR $\gamma$ -like action of PPFP. To assess feasibility, we performed thyroid MRIs on two PPFP;Pten $\Delta$  mice that were treated with pioglitazone and two that were not. Thyroid fat content was 13% in the two control diet mice, and 25 to 26% in the pioglitazone-treated mice. This optional MRI consent will allow us to assess whether a similar effect occurs in patients, and will provide another index of a response to pioglitazone.

Optional for enrolled patients who consent: Unstained tumor tissue slides from archival paraffin blocks, and/or fresh biopsy of tumor metastases, and/or peripheral blood (sera and/or DNA) will be collected and stored for potential analyses of tumor markers that may predict response or insensitivity to pioglitazone.

Optional radioiodine scan, and potentially radioiodine therapy, at the end of pioglitazone therapy. In non-PPFP thyroid carcinomas, thiazolidinediones have been shown to induce radioiodine uptake in some patients with otherwise non-iodine avid metastases, although in general the level of uptake has been clinically insignificant (11, 12), with rare exception (13, 14). It seems unlikely that pioglitazone would induce clinically useful radioiodine uptake in PPFP carcinomas, since in the mouse model the thyroid cells differentiate toward adipocytes, not thyrocytes. However, radioiodine uptake in patients should be determined to formally address this question. Patients with clinically significant uptake would be considered for radioiodine therapy, if clinically appropriate. This will be addressed in a separate follow-up protocol available to subjects completing this study.

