### **9.3 Sample Size/Accrual Rate**

We will accrue 15 evaluable patients, which allows for one drop out while still achieving the target enrollment of 14 patients. We expect to accrue ~4-5 patients per

year, for a total study accrual period of ~4 years.

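### With at most 14–15 patients, the exploratory logistic model of response on lipid change needs a small-sample method: the usual fit has little power and can lose its odds ratio to separation

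*Combined protocol and SAP*

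**What the plan says.** Section 9.2 sets out three things for tumor lipid: summaries overall and by response group, a paired test of change from baseline, and a model. On the model it says: "a logistic model will be used with the outcome being response". It labels this analysis exploratory and describes its single covariate in these words: "the independent predictor will be the lipid content change from baseline". It names no fitting method, test, interval type or fallback, and attaches no hypothesis, alpha or power to the model.

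The number of patients is bounded by the trial's size. Section 9.1 states: "Accrual of 14 evaluable patients at a 95% two-sided significance level will provide 87% power to detect a 40% response rate". That target is set against a low null rate, in the words "compared to the expected 5% or less". Section 9.3 adds: "We will accrue 15 evaluable patients, which allows for one drop out while still achieving the target enrollment of 14 patients". Section 2.3 makes the scan voluntary: "Optional for enrolled patients who consent: MRI will be used to assess fat content of the cancer metastases". Footnote j of the Study Calendar (4.7) restricts the follow-up lipid MRI to sites where lipid could be quantified at baseline. So 14–15 is a ceiling, and the documents do not say how far below it the number of MRI pairs will fall.

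**The concern.** At the target response rate, 14 patients yield 14 × 0.40 = 5.6 responders on average. Ordinary logistic regression is fragile at that size, in two ways.

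- If every responder's lipid change lies above (or below) every non-responder's, the maximum-likelihood odds ratio is infinite and its Wald p-value means nothing. The better lipid change discriminates, the more often this happens.
- When the groups do overlap, the Wald test still has very little power, because a large estimated slope comes with a large standard error.

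At stake is the only planned inferential analysis that ties lipid change to response, in a trial whose rationale (2.2) is that the drug turns tumor cells into adipocyte-like cells. The paired test asks a different question: whether lipid changes in patients as a whole.

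**Working it through.** **The plan's own figure.** Exact binomial, n = 14, null rate 5%, two-sided 5% level (2.5% in the upper tail):

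- P(X ≥ 3 | 0.05) = 0.0301, which exceeds 0.025, so the rule is 4 or more responses.
- P(X ≥ 4 | 0.05) = 0.0042.
- P(X ≥ 4 | 0.40) = 0.876, which agrees with the stated 87%.

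The 14 patients and the 40% rate can therefore be used as inputs.

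**Inputs.** From the documents: 14 patients (9.1) and a 40% response rate (9.1). Assumed, because the documents do not give them: 10 MRI pairs as a lower case; normal lipid change with equal SD in both groups; and a mean difference of 0 to 3 SD between responders and non-responders.

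**Separation.** A trial is separated when min(responders) > max(non-responders), or the reverse. With no association and k responders among n patients, 2 of the C(n, k) arrangements separate. For example, 2 / C(14, 5) = 2 / 2002 = 0.001. Averaging over k ~ Binomial(14, 0.40) gives about 0.3%. The other values come from simulation.

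**Power.** Each simulated trial was tested at a two-sided 5% level. Percentages are of all trials, and separated trials count as non-significant for the Wald test.

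| Difference | Separation, n = 14 | Separation, n = 10 | Wald rejects, n = 14 | Exact rank-sum rejects, n = 14 |
|---|---|---|---|---|
| 0 | 0.3% | 2.4% | – | under 4% |
| 1 SD | 3% | 11% | about 4% | about 32% |
| 2 SD | 25% | 42% | about 9% | 83% |
| 3 SD | 67% | 79% | about 4% | 98% |

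With 10 patients and 2 SD, the Wald test rejects in 0% and the rank-sum test in 61%. Repeat runs moved these entries by about a percentage point.

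Separation is not the whole of the Wald test's problem. At 2 SD and n = 14, about 75% of trials fit, and 9% / 75% = 12% of those reject. At 1 SD nearly all trials fit (97%), and about 4% reject.

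**A second parameterisation.** With a logistic model, a standard normal predictor and a 40% response rate:

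| Odds ratio per SD | 1 | 3 | 5 | 10 | 50 |
|---|---|---|---|---|---|
| Separation, n = 14 | 0.3% | 3.2% | 7.3% | 15% | 36% |
| Separation, n = 10 | 2.4% | 11% | 19% | 30% | 53% |

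At n = 14 and odds ratios of 3, 5, 10 and 50, the Wald test rejects in only 3% to 6% of trials. The likelihood-ratio test rejects in 45%, 65%, 84% and 97%, although it is slightly liberal (7.6% with no association).

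**After the fix.** Firth's penalised fit gives a finite estimate in at least 99.8% of trials at n = 14 and 99.0% at n = 10. The remainder have all or no responders.

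**Limits no method removes.**

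- If the true response rate is 5%, 0.95^14 = 49% of trials have no responder at all.
- With one responder among 14, the smallest two-sided exact p-value is 2/14 = 0.14.
- With 7 MRI pairs it is at best 2 / C(7, 3) = 2/35 = 0.057.

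**The case against.** A reader might infer that the planned analysis breaks whenever its hypothesis is true, or that the lipid–response finding would be lost. The documents do not support either reading.

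- **Size of effect.** A 1 SD difference is already a strong predictor (area under the ROC curve 0.76), and there separation is 3% at n = 14. It stays at or below about 15% up to an odds ratio of 10 per SD. Rates above one half need near-perfect discrimination (about 3 SD), or a strong association with few MRI pairs.
- **No source for 2–3 SD.** The only lipid figures are from mice: "Thyroid fat content was 13% in the two control diet mice, and 25 to 26% in the pioglitazone-treated mice". That compares treated with untreated animals, two per group. It says nothing about responders against non-responders among treated patients.
- **What is predicted.** Sections 1.3 and 7.1 concern a rise in lipid under treatment. The paired test addresses that, and separation does not touch it.
- **What survives.** The planned summaries by response group, which may include minimum and maximum, would show groups that do not overlap. What goes missing is a finite odds ratio and a valid test.
- **Method not named.** Section 9.2 specifies neither Wald tests nor unpenalised fitting. Firth or exact logistic regression would also be a logistic model, and the analysis is labelled exploratory.

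All of this stands, and it keeps the point small. It does not remove it. The usual fit is the likely default, it performs badly even without separation, and choosing a substitute after seeing the data is weaker than naming one now.

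**Conclusion.** The point holds as a minor one. At 14 patients or fewer, the usual maximum-likelihood fit with a Wald test has little chance of detecting a link between lipid change and response. The risk of no finite odds ratio grows with the strength of that link: about 3%, 25% and 67% at 1, 2 and 3 SD with 14 patients, and about 11%, 42% and 79% with 10. An exact rank-sum test on the same data keeps its 5% level and recovers most of the lost power at 2 SD (83% against 9%), and some at 1 SD (about 32% against 4%).

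These sizes rest on normal lipid change, a 40% response rate and assumed effect sizes and numbers of MRI pairs. The direction holds in every setting tried. With a low response rate, having no responders becomes the main obstacle, and it does not depend on the association. The primary endpoint and the paired lipid test do not change.

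**What to change.** Amend the model sentence in 9.2 to state that:

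- the association will be estimated by Firth penalised logistic regression with a profile-likelihood 95% confidence interval;
- lipid change will be compared between responders and non-responders with an exact Wilcoxon rank-sum test;
- only descriptive summaries will be reported if there are no responders (or if all patients respond), since no association can then be estimated.

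The analysis stays exploratory, and the number of MRI pairs and of responders should be given beside the result. The cost is one sentence and standard software, with no added patients, scans or visits.
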